 - f. The impact of other clinical characteristics on the outcomes: age, sex, comorbidities, sinusitis category.

3. Secondary culture endpoints

- a. The proportion of participants with S. pneumoniae on NP culture and the proportion of these with moderate and high resistance to penicillin
- b. The proportion of participants with moderately or highly resistant S penumoniae versus the others who achieve the primary and secondary clinical end points

4. Other questions

- a. What percentages were treated without meeting IDSA criteria; were excluded; and refused to participate?
- b. How frequently did participants guess correctly which medication they were taking, and were their guesses associated with outcomes?
- c. How did the change in SNOT-16 score—and individual questions—correlate with holistic ratings of improvement?
- d. How many patients had MRSA, and did carriage of MRSA affect outcomes?

Sample size determination

1. For improvement in symptoms at day 3: Garbutt et al, 2012, has 34% symptom improvement in controls (placebo); if a clinically meaningful impact of high-dose amoxicillin-clavulanate is to increase the response rate to 50% (giving a NNT of 7), 146 patients in each group would be required to have an 80% power to detect this difference (if it exists), with alpha .05 (http://www.sealedenvelope.com/power/binary-superiority/).

- The statistical consultant calculates, with alpha .05 only one-sided (not inappropriate since we are interested only in improvement), the needed sample would be 120 in each group.
- 2. For change in SNOT score: Garbutt et al, 2012 calculated that 100 patients in each group were needed to detect a true difference of .25. To detect the "clinically meaningful difference" of .50, fewer would be needed.

We propose, therefore, to aim for 150 patients in each group, i.e. a total of at least 300 participants in Med-Ped over a 2 year period.

In our patient population of over 10,000, we see about 10 patients a week with presumed acute sinusitis during the non-summer months—a total of over 600 last year with a diagnostic code of acute sinusitis--so we expect no problem in reaching our recruitment goal.

Procedure

Prior to enrollment

- 1. All clinicians achieve up-to-date certification in research ethics. Only those who are certified will enroll patients.
- 2. PI trains all the nurses and clinicians to be able to explain the study to patients, collect study data, and obtain informed consent.

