- 2. Research assistant (coordinator if possible) (if the resident on medical home rotation or a work-study student is not a feasible option)
 - a. Telephoning patients: 1 hour per patient x 300 patients @ \$20 per hour = \$6,000
 - b. Entering data: 100 hours a \$20 per hour = \$2,000.
- 3. Statistician: 20 hours @ \$100 per hour = \$2,000.
- 4. Cultures: estimate of \$100 per culture= \$30,000.
- 5. Duplication of forms: 600 @ 10 cents = \$60.
- 6. Study binders: 300 @ 50 cents = \$150.
- 7. Overall cost: \$44,550.
- 8. Funds will come from the AMC Med-Ped Research Fund, derived from private contributions and held by the Albany Medical Center Foundation, at the discretion of the Medicine-Pediatrics Division Head (currently [name]).

C. Subject Population

Source of participants: the patients of AMC Internal Medicine and Pediatrics, [name], who present with respiratory symptoms.

Total number of participants to be enrolled: 300.

Characteristics of population: adults, with no special populations (see Inclusion and Exclusion criteria above).

D. Data Analysis

See the Data Collection Sheet for a listing of the data that will be collected.

The Data Collection Sheets will be stored in a locked drawer in the PI's office.

The data will be entered by the research assistant (or Med-Ped residents or medical students doing work-study) into an Excel data base stored on a password-protected computer in the PI's office.

The Excel data base will be stripped of patient identifiers and transferred to SPSS by the statistical consultant, [name], who will, in turn, perform the analyses.

The primary analysis will be a simple chi-square analysis, with an alpha of .05%, of the difference in the primary endpoint (the proportion of participants who are "a lot better" or "no symptoms" at 3 days).

The analyses of the secondary outcomes (listed above) will depend on the nature of the data and be determined by the statistician.

E Risks

Risks of treatment

The side effects of treatment with amoxicillin/clavunate include:

- 1. Allergic reaction, usually minor, sometimes severe enough to send to the ED, very rarely resulting in death. Wikipedia's entry on anaphylaxis suggests death in about 1 out of 50,000 courses of penicillin.

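### Section D sets the primary chi-square test at .05% (0.0005), while the sample size for the same comparison uses alpha .05; probably a slip, but it sits in the primary decision rule

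*Combined protocol and SAP*

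**What the plan says.** Section D (Data Analysis) gives the only description of the primary test: "The primary analysis will be a simple chi-square analysis, with an alpha of .05", followed directly by a percent sign. The test compares the proportions who rate themselves a lot better or symptom-free at day 3. Section D leaves the methods for the secondary outcomes to the statistician.

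The sample-size part of Section B (Study Design) plans for the same endpoint and comparison. It takes a control response of 34% from the earlier placebo-controlled amoxicillin trial and a target of 50% on high dose, and states: "146 patients in each group would be required to have an 80% power to detect this difference (if it exists), with alpha .05". It then reports a second calculation by the statistical consultant, "with alpha .05 only one-sided (not inappropriate since we are interested only in improvement), the needed sample would be 120 in each group", and concludes: "We propose, therefore, to aim for 150 patients in each group".

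**The concern.** As written, .05% is 0.0005, one hundredth of the level used to size the trial. The plan has one primary endpoint at one time point and two arms. It describes no interim analysis and no multiplicity adjustment, so nothing in it would justify so strict a threshold.

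The affected sentence is the rule that decides whether the trial is positive. Any primary p-value between 0.0005 and 0.05 is significant under one section and not under the other. If the discrepancy were settled only after unblinding, the investigators would be relaxing the written threshold a hundredfold with the result in hand. That could be challenged even if the intention had always been 0.05.

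**Working it through.** **Inputs.** From the sample-size section: p1 = 0.34, p2 = 0.50, difference d = 0.16, power 80% (z = 0.8416), 150 per arm. From Section D: uncorrected chi-square test (the word used is simple), alpha as printed 0.0005. All 150 per arm are assumed evaluable.

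**1. Reproduce the plan's figure.** The unpooled two-proportion formula is

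n = (z_alpha + z_power)² × [p1(1 − p1) + p2(1 − p2)] / d²

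The variance term is 0.34 × 0.66 + 0.50 × 0.50 = 0.2244 + 0.2500 = 0.4744, and d² = 0.0256.

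- Two-sided 0.05: (1.9600 + 0.8416)² = 7.849; 7.849 × 0.4744 / 0.0256 = 145.4, so **146**. This is the plan's figure. The pooled-variance version gives 149.
- One-sided 0.05: (1.6449 + 0.8416)² = 6.183; 6.183 × 0.4744 / 0.0256 = 114.6, so 115. The pooled version gives 117. These are near the consultant's 120 and well below 146.

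So 146 is a two-sided 0.05 calculation, although the words two-sided never appear.

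**2. The same formula at the printed level.** Two-sided 0.0005: (3.4808 + 0.8416)² = 18.683; 18.683 × 0.4744 / 0.0256 = 346.2, so 347. The pooled version gives 354. Both are more than twice the planned 150.

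**3. Power at 150 per arm, 34% against 50%.** These figures come from summing exact binomial probabilities over all outcomes that the test would reject.

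| Test | alpha 0.05 | alpha 0.0005 |
|---|---|---|
| Critical chi-square, 1 df, two-sided | 3.84 | 12.12 |
| Power, uncorrected chi-square | 81.3% | 25.3% |
| Power, continuity-corrected | 78.0% | 21.7% |

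If 0.0005 were taken as one-sided, power (uncorrected) would be about 31%.

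**4. A trial that observes exactly its target.** 34% of 150 is 51, and 50% of 150 is 75. With 126 responders and 174 non-responders among 300:

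chi-square = 300 × (51 × 75 − 75 × 99)² / (150 × 150 × 126 × 174) = 300 × 3600² / 493,290,000 = 7.88, p = 0.0050

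With continuity correction the result is 7.24, p = 0.0071. Both exceed 3.84 and fall short of 12.12: positive at 0.05, negative at 0.0005.

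**5. Smallest winning result against 51/150 (uncorrected test).** At 0.05 the high-dose arm needs 68/150 (p = 0.045), a difference of 17/150 = 11.3 points. At 0.0005 it needs 81/150 (p = 0.00048), a difference of 30/150 = 20 points. That is more than the 16 points the plan calls clinically meaningful.

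**The case against.** The strongest reply is that this is a stray percent sign and no statistician would apply it. The documents themselves reveal the intended value: the sample-size section gives .05 for the same comparison, its 146 reproduces at that level, and the one-sided alternative uses .05 too. The power loss therefore belongs to an unlikely scenario, and the practical risk is close to nil. It can also be said that no calculation in the plan is wrong, since 146 is exact and 120 is within about 3% of the pooled 117. On sidedness, a simple two-by-two chi-square test is non-directional by construction, so Section D already settles the matter.

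Most of this stands. The slip is the likely explanation, the arithmetic of the plan is sound, and the power figures in steps 2 to 5 apply only if 0.0005 is used literally. The sidedness remark is a clarification and not an error: the plan mentions 120 but aims for 150.

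The reply does not remove the need for a correction. An intended value that has to be inferred from another section is not a prespecified threshold, and here the inference would overrule the one sentence that sets the primary rule. The range of results on which the two readings disagree includes the trial's own target result.

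**Conclusion.** The significance level in Section D is wrong as written and contradicts the basis of the sample size. It must be corrected before analysis. The importance comes from where the error sits, in the primary decision rule, more than from any likely loss of power. Applied literally, with 150 evaluable per arm and true rates of 34% and 50%, it would reduce power from about 81% to about 25% (78% to 22% with continuity correction). At the intended level the planned 150 per group is adequate for the stated 80% power with the uncorrected test. The contradiction itself and the reading of 146 as two-sided 0.05 follow from the documents; that the percent sign is a slip is an inference, though a strong one.

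**What to change.** In Section D, replace the stated level so that the primary analysis is a chi-square test at a two-sided alpha of 0.05 (5%). This is the level that reproduces 146 per group and fits the target of 150. Make the change, with a date, before the treatment allocation is linked to outcomes.

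As an optional clarification, note in the sample-size section that 146 is a two-sided calculation and that the one-sided 120 per group was not used.

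The cost is one line in Section D and perhaps one short note. No patients, data or analyses are added.

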Note that, unlike the IDSA guidelines, (2012) we do not plan automatically to treat with high-dose amoxicillin/clavunate all patients >65 or those who were hospitalized recently but not treated with antibiotics.

- 8. Suspicion of MRSA.
- 9. Drug warnings
 - a. Chronic kidney disease with estimated GFR < 30;
 - b. Hepatic impairment (not including isolated transaminase elevation <2 times normal);
 - c. Current mononucleosis (because of amoxicillin-induced rash);
 - d. History of antibiotic-associated colitis.
- 10. Need to hospitalize because of severity of infection, respiratory distress, or vulnerability of patient.

Treatment arms

- 1. Amoxicillin/clavulanate 1000/62.5 ER 2 tabs po bid for 7 days. (total pill burden 4 per day)
- 2. Amoxicillin/clavulanate 875/125 tabs 1 tab + 1 placebo tab po bid for 7 days (total pill burden 4 per day).

The duration of 7 days is in accordance with IDSA guidelines.

Both groups would be advised: 1) to instill saline into each nostril at least 2 times a day (1/4 tsp salt dissolved in 4 oz of distilled or boiled water, 1 teaspoonful administered into each nostril by sniffing, by syringe, or by Neti-pot; 2) to take acetaminophen for discomfort (not to exceed a total daily dose of 3 grams, or 2 grams if the patient drinks ETOH).

The pharmacist would prepare the medication bottles and randomize them (i.e., number the two sets of medication bottles as determined by a random number generator and keep the list of correlations between bottle number and actual contents).

Measurements (clinical)

- 1. Diagnostic criteria for acute sinusitis (as listed above): clinician to record these (including duration of illness and the category of acute sinusitis)
- 2. Initial additional data collection by nurse or clinician: previous side effects with antibiotics, antibiotics within past month, hospitalization in past 5 days, comorbidities (e.g., diabetes, heart disease, and lung disease)
- 3. Sinonasal Outcome Test-16 (SNOT-16) at days 0, 3, 10, and 30 (for validation of the form, see Garbutt et al, 2011, and Quadri et al, 2013).
- 4. Patients' summary assessment of their condition at days 3, 10, and 30: a lot worse, a little worse, the same, a little better, a lot better, no symptoms (as used by Garbutt et al, 2012).
- 5. Side effects at days 3 and 10
 - a. Diarrhea: none, mild, moderate, severe
 - b. Allergic reaction: rash without itching, rash with itching or hives
 - c. Other: abdominal pain, vaginal discharge and itching, other

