6. Drop outs:

- a. The participant can exit the study at any time, if much sicker, by going to the emergency department
- b. The participant can request, at any time, treatment with open-label antibiotic, e.g. doxycycline or levofloxacin (recommended by the IDSA), at the discretion of the clinician in the office or on call.
- c. The participant will be formally given this option at the day 3 telephone call.
- 7. Participants will be asked additionally at day 10
 - a. To guess which treatment they took (to evaluate adequacy of blinding, although it is expected that patients who get better faster will assume they took the higher dose).
 - b. To indicate how many doses they took. We will not ask for the bottles to be returned (which would require an otherwise unnecessary office visit for the participants).
 - c. To indicate if they would take that particular medication again if prescribed.
- 8. Participants will be asked additionally at day 30 if, and to what extent, they had persistence, resolution, or recurrence of symptoms.

Measurements (bacteriological)

Nasal cultures (anterior) will be performed on every patient. The cultures will be processed at the Albany Medical Center microbiology laboratory to assess:

- 1. What pathogens are present?
- 2. If S. pneumonia, what is its level of penicillin resistance?
- 3. If S. aureus, is it methicillin resistant?

Endpoints

- 1. Primary endpoint: Major mprovement of subjective symptoms at day 3 (i.e., 48-72 hours after starting treatment), rated as "a lot better" or "no symptoms."
- 2. Secondary clinical endpoints:
 - a. At least mild improvement in subjective symptoms at day 3: percent in each group rating their condition as "a little better," "a lot better," or "no symptoms"
 - b. Improvement in SNOT-16 score at day 3. Garbutt et al. (2012) indicate that a minimally important difference is 0.5 (on a scale of 0-3), although they used an effect size of 0.25 for their study size determination (requiring a bigger sample size). We will compare the percent in each group with average improvement \geq 0.5
 - c. The same comparisons at days 10 and 30 (one month).
 - d. Comparisons of side effects—diarrhea and others mentioned by participants on scale of 0=none to 3=severe--at days 3 and 10.
 - e. Percent of who dropped out because of side effects or inefficacy (switched to alternative antibiotic or went to the ED).

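### The primary day-3 test is valid and adequately sized, but it leaves the day-0 SNOT-16 unused; pre-specified adjustment could add about 0 to 6 points of power at almost no cost

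*Combined protocol and SAP*

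**What the plan says.** Section D (Data Analysis): "The primary analysis will be a simple chi-square analysis" of the proportion choosing one of the two best ratings on the six-point self-assessment at day 3. No covariate is named. The same sentence prints the alpha as .05%, whereas Sample size determination uses .05.

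Section B, Measurements (clinical), schedules the "Sinonasal Outcome Test-16 (SNOT-16) at days 0, 3, 10, and 30" and has the clinician record the diagnostic criteria, "including duration of illness and the category of acute sinusitis". Under Procedure, Enrollment, the patient fills out the SNOT-16 at step 5, the clinician marks the criteria at step 6, and the pre-numbered bottle is taken at step 10. The bottles are numbered from a random number generator (Treatment arms; Procedure, step 4); no stratification is described.

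Baseline characteristics appear only as secondary item 2f under Endpoints: "The impact of other clinical characteristics on the outcomes: age, sex, comorbidities, sinusitis category". Day-0 SNOT-16 is not in that list; it enters only through the secondary SNOT-16 improvement endpoint. Section D leaves the secondary methods to the statistician.

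**The concern.** A baseline measure that predicts the outcome can be used in the primary test to gain power from the same patients, and to correct the estimate when the arms happen to differ at baseline. The plan has such a candidate for every participant but does not use it in the primary analysis.

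The background text gives some reason to think that severity matters. It argues that earlier trials excluded the sickest patients, whose symptom scores had the most room to change.

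The power margin is thin. The target of 150 per arm is four above the calculated 146, and no allowance for missing day-3 telephone ratings is stated. If the arms differ visibly at baseline and no adjustment was pre-specified, adjusting afterwards would be open to challenge.

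**Working it through.** **Inputs.** Control rate 0.34, high-dose rate 0.50, 80% power, alpha .05, 146 per arm calculated and 150 targeted (Sample size determination). The plan does not state sidedness for the 146; two-sided reproduces it.

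**The plan's own figure.** Unpooled two-proportion formula:

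n = [0.34×0.66 + 0.50×0.50] × (1.960 + 0.842)² / 0.16² = 0.4744 × 7.85 / 0.0256 ≈ 145.5, so 146 per arm. This matches. The pooled version gives 149.

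**Power of the planned test at 150 per arm.** The average rate is 0.42, so √(2×0.42×0.58) = 0.698 and √0.4744 = 0.689.

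z = (0.16×√150 − 1.960×0.698) / 0.689 = (1.960 − 1.368) / 0.689 ≈ 0.859, giving power of 80.5%.

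**Power with adjustment, by approximation.** Let R² be the share of day-3 outcome variance explained by baseline, with effective n = 150/(1 − R²). The documents give no R², so these values are assumptions.

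| Assumed R² | Effective n per arm | Power |
|---|---|---|
| 0 | 150.0 | 80.5% |
| 0.05 | 157.9 | 82.5% |
| 0.10 | 166.7 | 84.4% |
| 0.20 | 187.5 | 88.4% |

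**Check by simulation.** 10,000 trials per setting, 150 per arm, one standardised baseline covariate; chi-square against the likelihood-ratio test from logistic regression.

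| R² | Log-odds per SD | Chi-square | Adjusted |
|---|---|---|---|
| 0 | 0 | 81.5% | 81.1% |
| 0.05 | 0.48 | 81.1% | 82.3% |
| 0.10 | 0.71 | 81.7% | 85.2% |
| 0.20 | 1.12 | 81.6% | 88.9% |

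Type I error was 4.6–5.1% for the chi-square and 4.7–5.4% for the adjusted test. A separate run on the log-odds scale gave adjusted power of about 81%, 82%, 83%, 84% and 88% at 0, 0.3, 0.5, 0.7 and 1.0 per SD, against about 81–82% unadjusted. The gain is therefore about 0 to 6 points up to 1.0 per SD. The R² = 0.20 rows lie just beyond that range.

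**Cost of a useless covariate.** With SNOT-16 and a three-level category both non-prognostic, 4,000 trials gave 81.0% for the chi-square and 80.3% adjusted, a loss of 0.7 points.

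**Chance imbalance.** The difference in baseline means has standard error √(2/150) = 0.1155 SD. A gap above 0.2 SD has z = 0.2/0.1155 = 1.73, so its two-sided probability is 8.3%. The shift in the unadjusted risk difference at a 0.2 SD gap is √R² × √(0.42×0.58) × 0.2, which is 2.2, 3.1 and 4.4 points at R² of 0.05, 0.10 and 0.20. The standard error of the difference is √(0.4744/150) = 5.6 points.

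**Missing ratings.** If 5% or 10% were missing (assumed), n is 142.5 or 135 per arm, and unadjusted power is 78.4% or 76.2%. Adjustment with R² of 0.05 or 0.10 respectively returns the effective n to 142.5/0.95 = 135/0.90 = 150, and power to 80.5%.

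**The case against.** The strongest reply is that nothing here is an error. The chi-square holds its type I error, matches the calculation that sized the trial, and meets its 80% target. All of that stands.

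Four stronger readings are tempting, and the documents do not support them.

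- **That power is being lost.** This would need evidence that baseline predicts the day-3 rating, and the documents give none. The endpoint is a self-rated change, already anchored to the patient's own starting point, so the link may be weak and the gain nil. At 0.3 to 0.5 log-odds per SD the gain is at most a point or two; gains of several points need stronger prediction.
- **That the plan itself says category influences outcome.** Item 2f poses a question for secondary analysis. It makes no claim of prognostic value, and because of it the plan does not ignore category altogether.
- **That the design offers no protection against imbalance.** Randomisation balances baseline in expectation, and the test's error rate already allows for chance differences. Adjustment protects the particular estimate obtained.
- **That category can simply be added.** Category 2b is defined by fever of at least 102 F, and exclusion 7a removes severe infection with the same fever threshold. The level may be very small, and its coefficient might not be estimable.

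On timing, the forms are collected or completed at steps 12 and 14, after the bottle is taken. The SNOT-16 answers are nevertheless given at step 5 and allocation is meant to be blinded, so this does not disqualify day-0 SNOT-16 as a covariate.

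**Conclusion.** The point holds as a missed, inexpensive improvement to a valid analysis. The planned test reaches about 80.5% power at 150 per arm, assuming 34% versus 50%, two-sided 5% and complete data. Adjusting for day-0 SNOT-16 would change that by about 0 to +6 points over an assumed 0 to 1.0 log-odds per SD, and would guard the estimate in the roughly 8% of trials with a baseline gap above 0.2 SD. The size of the benefit cannot be settled from the documents. The case rests on the asymmetry: a possible gain of several points against a loss of under one.

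Every power figure above takes alpha as .05. If the .05% in section D were applied literally (0.0005, two-sided), power at 150 per arm would be about 25%. That is a separate and larger matter, and it must be reconciled with Sample size determination.

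**What to change.** Before unblinding, amend section D as follows:

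1. Primary analysis: logistic regression of day-3 major improvement on arm and continuous day-0 SNOT-16. Report the standardised risk difference with 95% CI, and name the test that gives the primary p-value (the likelihood-ratio test is the one checked here).
2. Keep the unadjusted chi-square as a named sensitivity analysis.
3. Add sinusitis category only with a pre-stated rule for merging sparse levels, and state how a missing day-0 SNOT-16 is handled.
4. Separately, reconcile the printed .05% with the .05 used for sample size, and state whether the test is one- or two-sided.

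If the sponsor prefers to keep the chi-square as primary, the minimum is to name the adjusted model as a pre-specified sensitivity analysis.

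No new data are needed, since the secondary SNOT-16 endpoint already requires the day-0 score. Logistic regression is routine in SPSS; the standardised risk difference and its interval may need some extra programming. The price is under one point of power if the covariates prove non-prognostic.
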